6.4.2.4.1 Assignment to study drug

Depending on the TEAE onset, the AE will be assigned to a study drug. This is relevant for subjects with switch in study drug (i.e., treatment groups B1 and B2), as it may not be clear whether the TEAE is assigned to the study drug given in TP1 or to the study drug given in TP2.

- AEs with an onset before the start of TP2 will be assigned to the study drug given in TP1.
- AEs with an onset at or after the start of TP2 will be assigned to the study drug taken during TP2.

Consequently, AEs with an onset before start of TP2 which are ongoing during TP2 will not be assigned to the study drug given in TP2 unless the TEAE worsens after start of TP2. In case it is not clear to which study drug the AE will be assigned (for example, due to partially missing dates), those AEs will be assigned to vilaprisan (conservative approach).

6.4.2.4.2 Classifications of adverse events

Serious Adverse Events (SAEs) will be summarized in the same way as described for TEAEs.

Non-serious AEs will be shown on a summary table by primary SOC/PT.

Adverse events of special interest (AESI) will be identified in two different ways:

- 1) The investigators will assess all AEs to determine if they are AEs of special interest (AESIs) and document this in the eCRF. The following AEs are included:
 - a. HMB
 - b. Liver disorders
 - c. Endometrial disorders
 - d. Skin disorders
 - e. Adrenal disorders
- Adverse events will be categorized into AE groupings of special interest based on MedDRA groupings as defined within expert statement for compound vilaprisan (Selection of coding conditions applicable for AESIs as defined in the study protocols of vilaprisan phase II/III studies).

No.	AESI	Grouping
1	HMB (especially after end of treatment): HMB will be documented in detail throughout the study	MTG : [BMQ] Increased female genital bleeding[V8]
2	Liver enzymes	SMQ : Drug related hepatic disorders - comprehensive search (SMQ)[V29]
3	Endometrial hyperplasia (all subcategories according to WHO 2014 (and WHO 1994) classification	 PT selection: PT: Endometrial hyperplasia PT: Biopsy endometrium abnormal PT: Endometrial dysplasia PT: Endometrial metaplasia PT: Biopsy uterus abnormal
4	Endometrial thickening >18 mm	PT selection: PT: Endometrial thickening PT: Endometrial disorder

Table 6–2: List of AESIs in current expert statement based on MedDRA Version 22.1 (version 5.0, status 19FEB2020)

No.	AESI	Grouping
		PT: Endometrial hypertrophy
5	Adrenal neoplasms, Adrenal diagnoses related to cortical hyperfunction and cortical hypofunction	PBMQ : Adrenocortical gland pathology including tumors and related hormonal changes and conditions Vilaprisan (narrow scope)
		PT Addison's disease PT Adrenal adenoma PT Adrenal androgen deficiency PT Adrenal calcification PT Adrenal cortex dysplasia PT Adrenal cortex necrosis PT Adrenal cortex necrosis PT Adrenal disorder PT Adrenal gland abscess PT Adrenal gland cancer PT Adrenal gland cancer PT Adrenal gland cancer PT Adrenal gland cancer metastatic PT Adrenal gland tuberculosis PT Adrenal gland tuberculosis PT Adrenal gland tuberculosis PT Adrenal agland tuberculosis PT Adrenal haemotrnage PT Adrenal neoplasm PT Adrenal neoplasm PT Adrenal unsufficiency neonatal PT Adrenal suppression PT Adrenal suppression PT Adrenal thrombosis PT Adrenal tis PT Adrenal suppression PT Adrenal suppression PT Adrenal tis PT Adrenal suppression PT Adrenocortical carcinoma PT Adrenocortical insufficiency acute PT Adrenocortical insufficiency acute PT Adrenocortical insufficiency neonatal PT Adrenoleukodystrophy PT Adrenoleukodystrophy PT Congenital adrenal gland hypoplasia PT Congenital anomaly of adrenal gland PT Cortisol deficiency PT Gushingoid PT Cushingoid PT Cushingis syndrome PT Familial glucocorticoid deficiency PT Glucocorticoid deficiency PT Haemorrhagic adrenal infarction PT Hyperadrenocorticism PT Hyperadrenocorticism PT Hyperadrenocorticism PT Hyperotricoidism PT Hyperotricoid deficiency PT Haemorrhagic adrenal infarction PT Hyperadrenocorticism PT Hyperotricoidism PT Hyperotricoid deficiency PT Hyperotricoidism PT Hyperotricoid deficiency PT Hyperotricoid deficiency

Table 6–2: List of AESIs in current expert statement based on MedDRA Version22.1 (version 5.0, status 19FEB2020)

No. AESI		Grouping	
		PT Primary adrenal insufficiency	
		PT Primary hyperaldosteronism	
		PT Pseudohypoaldosteronism	
		PT Secondary adrenocortical insufficiency	
		PT Secondary aldosteronism	
		PT Steroid withdrawal syndrome	
		PT Triple A syndrome	
6	Cutaneous sarcomas	PT selection:	
		PT: Dermatofibrosarcoma protuberans	
		PT: Atypical fibroxanthoma	
		PT: Leiomyosarcoma	
		PT: Liposarcoma	
		PT: Skin angiosarcoma	
		PT: Kaposi's sarcoma	
		PT: Malignant fibrous histiocytoma	
		PT: Soft tissue sarcoma	

Table 6–2: List of AESIs in current expert statement based on MedDRA Version 22.1 (version 5.0, status 19FEB2020)

AESIs based on investigator assessment and AESIs based on MedDRA groupings will be presented separately. They will be presented by AESI group (if available), MedDRA primary SOC and PT and study drug. Summary tables for AESIs by maximum intensity and by worst outcome will be produced. Furthermore, listings will be provided.

6.4.2.5 Cervical smear

A frequency table for cervical smears findings at screening (Visit 1), FUP visit and safety closeout visit will be produced by treatment group.

6.4.2.6 Vital signs

Vital signs (heart rate, systolic blood pressure and diastolic blood pressure, and weight) will be summarized by treatment group and visit, including change from baseline where appropriate, using descriptive statistics. Boxplot for absolute values at each visit will be presented by treatment group. The time course by visit and by treatment group will be shown using line plots depicting the mean and 95% confidence interval (two-sided).

At the safety closeout visit the blood pressure will be measured as triplicates. The mean value of those will be reported in tables.

6.4.2.7 Anemia

Frequency presentations will be provided for moderate to severe anemia with hemoglobin $\leq 10.9 \text{ g/dL}$. Frequency tables with number of subjects and percentage will be displayed within treatment group and by Intervals C. If a subject has more than one hemoglobin measurement within a time interval of Intervals C, the smallest value (i.e. worst) will be used.

A listing will be provided for subjects with abnormal values.

6.4.2.8 Findings resulting from liver monitoring

Hepatic safety will be evaluated based on Intervals A and BL/Post baseline. The following parameters will be investigated in addition to the standard lab presentations:

- Aspartate aminotransferase (AST) (in U/L),
- Alanine aminotransferase (ALT) (in U/L),
- Alkaline phosphatase (AP) (in U/L),
- Bilirubin in serum (in mg/dL).

If a subject has more than one measurement of a parameter within the above specified time interval, the largest value (i.e. worst) will be used for the statistical analysis.

Frequency tables presenting number and percentage of subjects will be presented for the following categorizations:

- For ALT and AST, separately:
 - Normal (≤1×ULN); >1×ULN to <3×ULN; ≥3×ULN to <5×ULN; ≥5×ULN to <8×ULN; ≥8×ULN to <10×ULN; ≥10×ULN to <20×ULN; ≥20×ULN
 - \geq 3×ULN, \geq 5×ULN, \geq 8×ULN, \geq 10×ULN, \geq 20×ULN
- For ALT and AST combined (if at least one of ALT and AST falls into the category):

 \geq 3×ULN, \geq 5×ULN, \geq 8×ULN, \geq 10×ULN, \geq 20×ULN

- For bilirubin:
 - >1×ULN, >2×ULN
 - $\circ \leq 1 \times ULN; > 1 \times ULN \text{ to } \leq 2 \times ULN; > 2 \times ULN$
- For AP:
 - >1.5×ULN
 - $\circ \leq 1 \times ULN; >1 \times ULN \text{ to } \leq 1.5 \times ULN, >1.5 \times ULN$
- For combinations of ALT/AST and bilirubin:
 - >3×ULN for ALT or AST accompanied by >1.5×ULN in bilirubin (measured at any time point)
 - >3×ULN for ALT or AST accompanied by >2×ULN in bilirubin (measured at any time point)
 - $\circ \geq 3 \times ULN$ of ALT or AST accompanied by $\geq 2 \times ULN$ of bilirubin (measured within 30 days afterwards) (Hy's Law criteria). The event will be assigned to the time interval of the ALT/AST elevation.

Kaplan Meier estimates for the time to $ALT > 3 \times ULN$ will be derived for each considered time interval. If no such an increase is observed within the considered time interval, the observation is censored at the end date of the time interval. Tables with the number of

subjects under risk, cumulative number of subjects with $ALT > 3 \times ULN$, and estimated probability for an event including 95% confidence intervals (two-sided) will be presented per 28 days. Furthermore, Kaplan Meier plots will be provided.

eDISH plots (x-axis: maximum of ALT or AST, resp., within time interval; y-axis: maximum of total bilirubin within 30 days thereafter) and a scatter plot (x-axis: maximum ALT within time interval; y-axis: maximum AST within time interval) will be provided for each considered time interval.

If a patient has $ALT \ge 3 \times ULN$ at any time point, a plot for her individual time course in the following laboratory parameters will be presented: ALT, AST, bilirubin, and AP relative to ULN over time. It will be indicated within the plot on which days the study drug was taken (i.e. start and stop of treatment periods). Furthermore, listings will be provided with results relative to ULN for liver-related parameters, i.e. ALT, AST, bilirubin, AP.

6.4.2.9 Liver symptom inquiry

Before the implementation of Integrated Clinical Study Protocol, version 5.0, investigators were asked to regularly inquire about symptoms that according to their medical judgement may indicate liver disturbance and document the result of this inquiry in the respective eCRF page. This data will be listed only.

6.4.2.10 Findings resulting from adrenal monitoring

Subjects were asked to undergo scheduled adrenal monitoring at the safety closeout visit. The adrenal monitoring comprises the following assessments:

- Adrenal gland imaging
- Laboratory testing
- Signs and symptoms suggestive of hypercortisolism, hyperaldosteronism

All tables generated within this adrenal monitoring section will contain the absolute number of subjects and percentage among subjects who performed the safety closeout visit.

An *overview* table will be provided. This table includes the number and percentage of subjects taking part at the specific adrenal monitoring assessments. The following numbers and percentages of subjects will be provided in addition:

- Subjects with abnormal result in at least one of the assessments.
- Subjects with abnormal result for each specific assessment separately.
- Subjects for whom an external expert recommendation was obtained. Among those, also the number and percentage of subjects with any findings suspicious of an adrenal disorder and recommendation for further handling will be provided.
- Subjects who have seen a local specialist (including information on type of specialist).

Details of the *final diagnosis by the expert panel* will be provided in another table. This table contains the number and percentage of subjects assessed by an expert, subjects needed expert panel meeting, subjects where expert panel met, and subjects with at least one diagnosis by the expert panel. Among those, the following numbers and percentages of subjects will be provided:

- Subjects with agreement of the diagnosis among all three experts.
- Subjects with a specific diagnosis (multiple diagnoses are possible).

A listing of subjects with other diagnosis (i.e. diagnosis entered by the expert panel in a text field) will be provided. A listing of subjects with adrenal tumor will presented as well. It includes diagnosis, time from last study drug until date of panel assessment and possible causal relationship to study drug. Cases where the three experts did not agree on a diagnosis, are presented in a separate listing including also the diagnosis of the local specialist.

A third table will summarize the *diagnosis by a local specialist*. This table contains the number and percentage of subjects with at least one diagnosis by the local specialist. Among those, the numbers and percentages of subjects with a specific diagnosis (multiple diagnoses are possible) will be reported.

A listing of subjects with other diagnosis (i.e. diagnosis entered by a local expert in a text field) will be provided as well as a listing of reasons if a local specialist consultation did not take place despite referral.

A listing of local laboratory measurements with reference ranges will be provided (no descriptive analyses will be performed on those).

A table with *results of the adrenal glands imaging* will be provided. This table contains the number and percentage of subjects who did and who did not perform adrenal imaging (and reasons if not performed), and who have at least one evaluable image. Among subjects having performed adrenal glands imaging the type of procedure (e.g. computed tomography [CT] scan with contrast) will be reported. The following numbers and percentages of subjects will be derived among subjects with at least one evaluable image:

- Subjects with one or two evaluable lateralities.
- Subjects with adrenal mass (if yes, in one or in both adrenal glands).
- Subjects with specified diagnostic benign imaging features.
- Subjects with specified indeterminate imaging features.

Reader results where an adjudicator was needed due to discrepant diagnoses between the two readers will be provided in a listing.

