##### 9.6.1.2.3 Causal relationship

The assessment of the causal relationship between an AE and the administration of treatment is a decision to be made by the investigator, who is a qualified physician, based on all information available at the time of the completion of the eCRF.

The assessment is based on the question whether there was a “reasonable causal relationship” to the study treatment in question.

Possible answers are “yes” or “no”

An assessment of “no” would include:

1. The existence of a highly likely alternative explanation, eg, mechanical bleeding at surgical site.

or

2. Non-plausibility, eg, the subject is struck by an automobile when there is no indication that the drug caused disorientation that may have caused the event; cancer developing a few days after the first drug administration.

An assessment of “yes” indicates that the AE is reasonably associated with the use of the study treatment.

Important factors to be considered in assessing the relationship of the AE to study treatment include:

- The temporal sequence from drug administration: The event should occur after the drug is given. The length of time from drug exposure to event should be evaluated in the clinical context of the event.
- Recovery on drug discontinuation (de-challenge), recurrence on drug re-introduction (re-challenge): subject’s response after de-challenge or re-challenge should be considered in view of the usual clinical course of the event in question.
- Underlying, concomitant, intercurrent diseases: Each event should be evaluated in the context of the natural history and course of the disease being treated and any other disease the subject may have.
- Concomitant medication or treatment: The other drugs the subject is taking or the treatment the subject receives should be examined to determine whether any of them might have caused the event in question.
- Known response pattern for this class of drug: Clinical/preclinical
- The pharmacology and PK of the study treatment: The PK properties (absorption, distribution, metabolism and excretion) of the study treatment, coupled with the individual subject’s pharmacodynamics should be considered.

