### **9.6.3.8 Adrenal monitoring**

A robust adrenal safety monitoring program is implemented in all ongoing vilaprisan studies with this protocol amendment.

A plan for subjects showing adrenal neoplasms or hormonal abnormalities has been developed with the input of external endocrinology experts, see Adrenal monitoring algorithm below.

A panel of three external clinical adrenal gland experts has been set up, that will support and guide further evaluations and/or referral to local specialists in case an abnormality is detected in a study subject. The assessment by the experts will be performed in 2 steps:

[figure not shown]
- A safety assessment of cases showing abnormalities will be performed by one of these experts. The results of this assessment will be available in time to document
  - Any relevant finding that requires further diagnostic or therapeutic measures according to local medical practice
  - Absence of clinically relevant adrenal findings before the subject discontinues from the study.

In case of a local specialist consult, the work-up and results will be captured in a dedicated CRF page.

- In addition, the expert panel will perform a central evaluation of all cases after the outcome of the local specialist referral or other evaluations is available. The panel will meet once a sufficient number of cases is available to perform a comprehensive data analysis by using uniform diagnostic standards and classifications (see also Adrenal Monitoring Manual).

The further details of adrenal monitoring are described in the Adrenal Monitoring Manual.

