### 9.6.3.8.1 Timing of adrenal monitoring

Subjects will undergo scheduled adrenal monitoring at the safety closeout visit.

Signs and symptoms possibly related to hypercortisolism (such as Cushing’s syndrome, and hirsutism/virilization) or hyperaldosteronism will be documented on a dedicated CRF page (see Section 9.6.3.8.4).

Adrenal monitoring also needs to be performed in subjects who started treatment and have completed or discontinued the study before or during the temporary pause. After re-

consenting, data related to adrenal monitoring and their results are to be documented in the CRFs, and if applicable, same applies to any related AEs and respective concomitant medications. At least three attempts should be made by the site to get in contact with such subjects. The attempts should be documented in the subject file.

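### The adrenal-tumour listing times each case from last study drug to the panel assessment, so an unspecified review lag is included and the interval may start from placebo

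*SAP*

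**What the plan says.** SAP 6.4.2.10 plans a listing of subjects with adrenal tumour. It contains the diagnosis, the "time from last study drug until date of panel assessment", and whether the tumour may be causally related to study drug. The section names no interval to imaging, detection or first diagnosis.

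Protocol 9.6.3.8 describes two steps. One expert first makes a safety assessment of each abnormal case. Then "the expert panel will perform a central evaluation of all cases after the outcome of the local specialist referral or other evaluations is available". On timing it adds: "The panel will meet once a sufficient number of cases is available to perform a comprehensive data analysis". It sets no maximum delay. On detection, Protocol 9.6.3.8.1 says: "Subjects will undergo scheduled adrenal monitoring at the safety closeout visit". Protocol 9.6.1.6 recognises three sources of a tumour diagnosis: the central MRI read, the adrenal expert and the local specialist.

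Among the factors for judging causality, Protocol 9.6.1.2.3 states: "The length of time from drug exposure to event should be evaluated in the clinical context of the event".

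**The concern.** The protocol's causality guidance looks at time from exposure to the event. The listing shows time from exposure to a review of the event, next to the causality column. A reader of the study report would naturally take the figure as time to detection.

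Adrenal cortical tumours in female rats were among the findings behind the pause (Protocol Section 3), and the closeout examinations are meant to help show whether vilaprisan plays a role in such tumours. Few cases are likely, so each line of the listing will be read closely.

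The starting date is a second, smaller problem. Group B2 was assigned vilaprisan and then placebo (Protocol 7.1). For a B2 subject who started Treatment Period 2, the last study drug is placebo.

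**Working it through.** The plan gives no figure to reproduce. The check is date arithmetic and a comparison of sections.

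**1. What the listed interval contains.** Let E be the last study drug intake, D the first image or test showing the finding, and P the panel assessment.

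- Listed interval = P − E = (D − E) + (P − D).
- D − E is time from last dose to detection. P − D is the review lag.
- P cannot precede D, because the central evaluation follows the other work-up. The lag is therefore zero or positive, and the documents do not bound it.
- D cancels out of P − E. Two women with the same last-dose date who are assessed on the same panel date get the same listed value, whenever each was imaged.

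**2. Illustration of size.** Inputs from the documents:

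- Version 4.0 (the pause) is dated 11 DEC 2018 and Version 5.0, which introduced adrenal imaging, 20 NOV 2019 (Protocol cover page).
- A treatment period is 84 days (Protocol 7.1), and an ongoing period could be completed after the pause (SAP Section 3).

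Take a subject who starts a period on 11 DEC 2018 and completes it. This is illustrative, because sites may have implemented the amendment on other dates.

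- Last dose: 11 DEC 2018 + 83 days = 04 MAR 2019.
- Earliest imaging under Version 5.0: 20 NOV 2019, so D − E = 261 days.

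The lags below are assumptions; no document gives one.

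| Assumed lag P − D (days) | Listed interval (days) | Share that is review lag |
|---|---|---|
| 0 | 261 + 0 = 261 | 0% |
| 30 | 261 + 30 = 291 | 30/291 = 10% |
| 90 | 261 + 90 = 351 | 90/351 = 26% |
| 180 | 261 + 180 = 441 | 180/441 = 41% |
| 365 | 261 + 365 = 626 | 365/626 = 58% |

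**3. The starting date in group B2.** If a B2 subject completes an 84-day placebo period, her last study drug falls (break length + 84) days after her last vilaprisan intake. Here the listed interval is too short relative to last vilaprisan, while the review lag makes it too long. The net direction cannot be stated in general. SAP Section 3 says too few patients started Treatment Period 2 to support conclusions, so few subjects can be affected in this way.

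**4. How the SAP anchors other findings.** An ovarian cyst episode starts when the structure is first observed (6.4.2.2). A Hy's Law event belongs to the interval of the transaminase elevation (6.4.2.8). Adverse events are assigned to study drug by onset (6.4.2.4.1). The adrenal listing alone is anchored to a review date, and no reason is given.

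**The case against.** The strongest reply is that this is one descriptive listing. The SAP labels the interval by its true end point, never calls it latency, and sets it beside the panel's own diagnosis. No document says that it feeds a causality decision, and Protocol 9.6.1.2.3 governs the investigator's adverse event assessment, not this table. Adrenal tumours are also reported as SAEs, with AESI listings planned (SAP 6.4.2.4.2), so relevant dates may appear there. Time to first image is not latency either, because imaging began only with Version 5.0 and takes place at closeout. All of this limits the impact. It does not supply a detection interval in the listing that carries the causality column, and the SAP does not promise one there.

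Some stronger inferences are tempting but are not supported:

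- **The figure shows only meeting scheduling.** It also contains the time from last dose to detection, which is 261 days in the illustration. The SAP also counts separately "subjects needed expert panel meeting, subjects where expert panel met", so an assessment may be dated without a meeting. Review timing is the safer description.
- **Batching adds the same delay to every case.** A shared panel date gives a different lag to women detected on different dates.
- **The longer interval makes tumours look less drug-related.** Nothing in the documents says so. The protocol's only cancer example treats a very short time after first dose as implausible.
- **An imaging date exists for every tumour.** SAP 6.4.2.10 provides for subjects without imaging, and a diagnosis may come from the expert or the local specialist.

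**Conclusion.** The point holds, and it is minor. The listed interval for every adrenal tumour runs to a review date, so it is not the time from exposure to detection. In some B2 subjects it also does not start from vilaprisan. The size of the lag and any effect on the causality judgement cannot be derived from the documents; the 10% to 58% shares rest on assumed lags of 30 to 365 days and one illustrative subject. The conclusion assumes that the panel assessment date is the date of the central evaluation in Protocol 9.6.3.8. The Adrenal Monitoring Manual and the table specifications, which might refine this, were not available. No test, estimate or confirmatory result is affected.

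**What to change.** In the SAP 6.4.2.10 listing of subjects with adrenal tumour:

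- Report the intervals from first and from last vilaprisan intake to the date of the first image or test showing the adrenal finding. If there is no image, use the date of first diagnosis.
- Mark these intervals as not applicable for a B1 subject who took only placebo.
- Keep the panel assessment date as a separate column.
- Add a footnote that detection time is largely determined by the safety closeout visit and is not true onset.

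The cost is minor rewording of the SAP and table specifications and one or two extra columns. Dosing dates are already used in the SAP. The availability of imaging or first-diagnosis dates for each case should be confirmed against the eCRF.
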